GHRI	Group Health Research Institute
ICH	International Conference on Harmonisation
IRB	Institutional Review Board
NIDCR	National Institute of Dental and Craniofacial Research, NIH, DHHS
NIH	National Institutes of Health
PPA	Point Prevalence Abstinence
RCT	Randomized Controlled Trial
SAE	Serious Adverse Event/Serious Adverse Experience
UC	Usual Care
UP	Unanticipated Problem
US	United States

PROTOCOL SUMMARY

Title:

Oral Health 4 Life: Promoting Oral Health among Tobacco Quitline Callers

Précis:

Promoting better oral health is a public health priority. Tobacco users, in particular, are at high risk for oral disease compared to non-smokers both as a result of their smoking and the fact that many fail to meet recommendations for basic oral health care, including daily oral hygiene and regular professional dental care.

The current study will test the effectiveness of a multi-modal behavioral intervention (the Oral Health 4 Life program) targeted to smokers who are ready to quit smoking and seeking services through tobacco quitlines. Quitline callers have made a commitment to improving their health and our research suggests most are receptive to learning how to improve their oral health, as well. Moreover, there is reason to believe that promoting basic strategies such as brushing, flossing, or rinsing with fluoride mouthwash in response to cigarette cravings or having a professional dental cleaning to remove tobacco stains could promote better oral health and bolster attempts to quit smoking. Thus, an integrated oral health promotion-tobacco cessation program could have dual benefits.

We will partner with Alere Wellbeing, the nation's largest provider of tobacco quitline services. Leveraging Alere's infrastructure for this intervention increases the likelihood the intervention could be disseminated, if effective.

Smokers (n ~ 742; minimum of 10 and up to ~30 pilot participants and ~712 main trial participants) will be recruited when they call to enroll in services. Eligible smokers who have not received recent dental care will be randomized to either usual care quitline intervention plus control text messaging or an enhanced program which integrates standard tobacco cessation counseling with a multi-modal, behavioral oral health promotion program. The enhanced program includes behavioral counseling, mailed written materials, access to online materials and resources, support/ outreach via text messaging, and referral information for affordable local dental care. Follow-up assessments will be conducted by phone at 2 and 6 months

post-enrollment. Primary outcomes are: receipt of professional dental care following enrollment [yes/no] and self-reported 7 day point prevalent smoking abstinence at 6 months [yes/no]. We hypothesize that persons who receive the enhanced program will be more likely to see a dentist and to quit smoking.

Secondary outcomes and process measures of interest include: whether a participant either receives professional dental care or has scheduled a future dental appointment at 6 months, smoking abstinence at 2 months, and changes in oral health knowledge and relevant attitudes (self-efficacy, motivation, perceived oral disease severity, and outcome expectations/perceived benefits of oral hygiene) at 2 and 6 months. The incremental cost of delivering the Oral Health 4 Life program will also be examined.

Objectives: Primary Objective: To assess the effects of the proposed behavioral intervention on tobacco abstinence and utilization of professional dental services (primary outcomes).

Secondary Objectives:

- Assess the impacts of the enhanced intervention on key secondary behavioral outcomes and select intermediate outcomes/process measures that could mediate treatment effects.
- Determine the effectiveness of the proposed enhanced intervention, whether it warrants dissemination to smokers through tobacco quitline programs nationally in the current form, or whether further refinement and evaluation are warranted.
- Calculate the incremental cost of adding the Oral Health 4 Life program to usual quitline care and create a decision support tool that quitline sponsors (i.e., potential purchasers of the program) can use to inform decisions about whether to offer the program.

Primary Outcome: a) Receipt of professional dental care following enrollment [yes/no]; and b) self-reported 7 day point

prevalent smoking abstinence at 6 months [yes/no; missing cases imputed as smokers].

Secondary Outcomes: a) Whether a person has seen a dental care provider since enrollment or scheduled a future dental appointment at 6 months; b) 7 day point prevalent abstinence at 2 months (with missing cases imputed) and smoking abstinence at the 2 month and 6 month follow-up among respondents only (no missing imputation); c) changes in oral health knowledge; d) and relevant attitudes (self-efficacy, motivation, perceived oral disease severity, and outcome expectations/perceived benefits of oral hygiene) at 2 and 6 months. The incremental cost of delivering the Oral Health 4 Life program will also be examined.

Population:	Male and female adult smokers (n ~ 742) aged 18 or older will be recruited from participating US tobacco quitlines in Oregon, Louisiana, and Nebraska. Those who have not used dental care services in the past 6 months and meet other study criteria (sections 5.1& 5.2) will be eligible to enroll.
Phase:	III
Number of Sites:	Study activities will be conducted at two research sites: Group Health Research Institute (GHRI) and Alere Wellbeing, each located in downtown Seattle. However, participants will be recruited from multiple state tobacco quitline programs managed by Alere.
Description of Intervention:	Participants will receive a multi-modal, behavioral intervention offered in conjunction with standard care tobacco quitline intervention. Oral health promotion intervention will be delivered via behavioral phone counseling, mailed materials (educational self-help information and oral health aids [e.g., toothbrush, floss, etc.]), educational content delivered via a log-in secured study website (OralHealth4Life.com), and additional education and supportive encouragement offered via a series of text messages. Participants will also receive referral information for low cost dental care in their geographic area.
Study Duration:	We estimate it will take about 30 months to complete the proposed RCT. Recruitment will begin at approximately month 7 of the grant phase, depending on the required timeline for finalizing the study materials in collaboration with NIDCR staff. ~742 participants will be enrolled. The first ~10 participants will constitute a vanguard wave. Program refinements will be made,

[figure not shown]
as needed, based on our experience with these participants. Consequently, we have planned a priori to exclude these individuals from the final analytic sample, resulting in a final intent to treat sample of ~712. Recruitment, intervention delivery, and follow-up assessments will continue through approximately month 36. The remainder of the grant period (months 37-48) will be devoted to data management, analyses, interpretation, and dissemination of findings.

Subject Participation Duration:	Each participant will be enrolled for a period of 6 months.
Estimated Time to Complete Enrollment:	We estimate it will take one month to recruit the vanguard participants and up to, but not more than, twenty-three additional months to recruit the remaining participants. Recruitment pace will depend on the call volume at the participating quitlines. If needed, this will be titrated to ensure that the timing and volume of the counseling and follow-up surveys do not outpace staff capacity to complete these on schedule.

Schematic of Study Design (NOTE: Reflects final analytic sample, n ~ 712):

Cohort	Arm 1	n~ 356	Usual Care (UC)
	Arm 2	N~ 356	Enhanced Intervention

Diagram 1: Study Flow for RCT

NOTES: Intervention call timing is tailored for each person, based on their chosen Quit Date. As a result, calls may or may not be complete prior to the 2 month follow-up for all participants. The chosen target Quit Date will also affect the timing of the text messaging. For more detail on the timing of the intervention events, see Appendix A Schedule of Events.

Table 1. Overview of Study Activities by Site

	GHRI	Alere Wellbeing
Recruit, screen, & enroll participants		X
Collect baseline data		X
Provide phone counseling & usual care tobacco cessation services		X
Mail usual care tobacco cessation materials		X
Mail consents, study welcome letters & oral health promotion materials	X	
Manage text messaging	X	
Maintain study website(s)	X	
Conduct follow-up assessments	X	
Mail participant incentives	X	
Conduct fidelity monitoring	X	X
Provide regular data feeds to GHRI		X
Monitor automated data integrity	X	
Provide final cost data	X	X
Management of final analytic datasets	X	
Data analyses	X	
Interpretation of study findings	X	X
Primary responsibility for publication & dissemination of results	X	

2 INTRODUCTION: BACKGROUND INFORMATION AND SCIENTIFIC RATIONALE

2.1 Background Information

Oral disease is a significant public health threat.

Oral disease affects millions of people in the US. It includes common oral diseases such as periodontitis and dental caries, and less common oral and pharyngeal cancers. Together these diseases exact a large human toll. Oral disease not only results in unnecessary pain, potential physical disfigurement, and emotional suffering, it puts individuals at greater risk for subsequent morbidity and mortality¹. Treating acute oral disease and preventing the onset of future oral disease are important public health goals.

Smokers are a priority population for oral health promotion.

Tobacco use accounts for an estimated 90% of oral and pharyngeal cancers, and smoking is the second leading modifiable risk factor for periodontitis.⁶ According to the National Health and Nutrition Examination Survey (NHANES)⁷, current smokers have a higher prevalence of untreated tooth decay (35.0%) than those who never smoked (18.6%) or former smokers (17.7%). Tooth loss is also strongly associated with smoking and more common in current than former or never smokers.⁸ Two-thirds of current US smokers have at least one unmet dental need compared to 55% of non-smokers.⁹ Two-thirds do not have an annual dental visit and, in general, fewer smokers see the dentist than non-smokers.^{10, 11} In addition, many smokers fail to seek routine health care^{12, 13}, have high rates of alcohol use¹⁴⁻¹⁷, poor diets¹⁸, and low levels of important micronutrients due to oxidative stress from smoking and dietary choices¹⁹—all contributing factors in oral disease. Among smokers treated through tobacco quitlines, we have observed similarly high levels of self-reported oral disease (based on current symptoms) and sub-optimal use of dental care and routine oral hygiene behaviors.^{20, 21} In short, smokers represent an important target group for oral health promotion.

2.2 Rationale

Combined oral health promotion and smoking intervention could have synergistic effects.

Promoting better oral health care in conjunction with quitting smoking could enhance efforts to stop smoking and vice versa. Best practice smoking cessation counseling is grounded in cognitive behavioral therapy (CBT).^{22, 23} Standard CBT for nicotine dependence in part teaches smokers to use distraction techniques as a means for managing cravings and resisting the urge to smoke. This technique can be tailored to also promote better oral health by directing smokers to chew sugar-free gum, brush their teeth with fluoride toothpaste, gargle with a fluoride mouth rinse, or floss in response to cravings to smoke. We've found these distraction techniques to be effective

for many people because they offer a distraction to thinking about smoking, introduce taste sensations which are incompatible with smoking, and engage the smoker in behaviors which are physically incompatible with the act of smoking (e.g., one cannot smoke and brush their teeth concurrently). These are important behavioral therapeutic goals. Importantly, each behavior also serves a dual benefit of reducing plaque and promoting better tooth and gum health.^{1, 24-26} Practicing these behaviors during the quit process could lead to their greater integration in one's normal daily hygiene routine by creating mastery experiences, building individual's confidence (self-efficacy) in their ability to engage in these behaviors, and creating positive outcome expectations (e.g., brushing my teeth makes my mouth feel clean and lessens my desire to smoke). These are all important mediators of behavior change.

Moreover, research shows a positive association between smokers' concerns about tooth discoloration caused by tobacco use and their interest in quitting smoking.²⁷ Thus, smokers ready to quit may be particularly receptive to advice to have their teeth cleaned around their quit date, to remove tobacco stains and start their new life looking like the non-smoker they will soon be. Smokers who might not otherwise seek professional dental care may be willing to do so at this time, particularly if the enhanced intervention includes referral to affordable local dental care (as the Oral Health 4 Life program does). And having one's teeth cleaned could provide continued motivation to remain quit. In other words, we believe that a dual focus on better oral health and tobacco cessation could have potentially powerful synergistic effects to improve cessation rates, promote professional dental care utilization, and alter routine oral hygiene care.

Partnering with state-funded tobacco quitlines to promote oral health.

The Office of the Surgeon General⁶ and Centers for Disease Control and Prevention¹ have each called for greater partnerships between the public and private sector and inclusion of health care organizations, health insurers, and health professionals in efforts to promote oral health. With regard to smokers and tobacco users, the emphasis has been placed on empowering dentists and dental hygienists to intervene with their patients to promote tobacco abstinence. However, oral health care professionals often have limited time and resources to provide behavioral intervention and these efforts fail to reach individuals who do not visit a dentist (which may be more than half of smokers calling state-funded tobacco quitlines).²¹ Moreover, many dental professionals are not formally trained in behavioral counseling and simply providing oral health education alone does not result in lasting behavior change.²⁸⁻³³

A complementary strategy for intervening with smokers, particularly those not routinely seeking dental care, is to integrate oral health promotion efforts into tobacco quitline programs. Tobacco quitlines provide behavioral counseling for tobacco cessation, primarily through proactive counseling calls (i.e., calls initiated by the quitline based on a pre-determined call schedule) with supplemental outreach via online materials, mail,

and/or text messaging. Quitlines have been shown to be an effective public health intervention for smoking cessation.³⁴⁻³⁷

All 50 US states offer free tobacco quitline programs funded through state revenues and/or the CDC. All callers are eligible for at least a single counseling call, with uninsured callers and other special populations (e.g., pregnant smokers) eligible for multi-call programs. According to data from the North American Quitline Consortium, nearly 440,000 people received services from state-sponsored quitlines in 2010.³⁸ Across the various state quitline contracts serviced by Alere Wellbeing, more than 279,000 people received services in 2012, nearly 352,000 people received services through all of their service contracts combined in 2012, and more than 2,235,000 people have received services from this company to date. While the largest in the US, Alere is only one of several US tobacco quitline vendors. Thus, tobacco quitlines represent an efficient way to reach a large number of smokers who are also in need of oral health promotion. Furthermore, our research demonstrates quitline callers are interested in improving their oral health (see section 2.3 below).^{20, 21} And because quitline callers are actively seeking treatment, these individuals may be more amenable to an oral health promotion program delivered in conjunction with their tobacco counseling. That is, reaching tobacco users when they enroll in quitline services may represent a 'teachable moment' for change.

Significance & Impact Summary

There is good reason to expect promoting positive oral health care in conjunction with smoking cessation will improve abstinence rates and it is known that quitting smoking improves oral health outcomes.¹ Additionally, increasing utilization of professional dental care can reduce risk of disease and allow existing pathology to be treated, possibly preventing more serious and costly future disease. Thus, it is reasonable to promote better oral health in tandem with nicotine dependence treatment. Working through the tobacco quitlines is an innovative strategy to test this approach. More importantly, this partnership enhances the public health significance of the research because our intervention has been carefully designed in collaboration with the largest US tobacco quitline provider so it can be disseminated on a national level, if effective. As such, this work holds the potential to improve oral health care, cessation rates, and oral health outcomes among hundreds of thousands of smokers nationwide. Finally, this study will provide important information about the added cost of the Oral Health 4 Life program to inform quitline purchasers' (payers) future decisions about offering this program.

Innovation

Good oral health is good public health. Promoting better oral health among smokers should not be shouldered by professional dental care professionals alone. This study represents the first time tobacco quitlines, or any nicotine dependence treatment program to our knowledge, have been leveraged to promote better oral health care and

smoking cessation. This study will provide critical information about the effectiveness and additional cost of this public health intervention strategy for promoting abstinence and use of dental health services. It also offers an important complement to ongoing efforts in many dental care settings to promote smoking cessation and refer patients to the tobacco quitlines.

2.3 Potential Risks and Benefits

2.3.1 Potential Risks

Potential risks include breach of confidentiality and discomfort associated with answering research questions.

Persons who stop smoking may experience symptoms of nicotine withdrawal (e.g., irritability and mood changes, headaches, trouble sleeping, constipation, cravings to smoke). These are typically transient and resolve within a few weeks after cessation. Nicotine withdrawal symptoms may be reduced in smokers who use nicotine replacement therapy (NRT) as an adjunct to the quitline counseling; however, they may experience side-effects associated with NRT patch including headaches, nausea, trouble sleeping, and rash/irritation at the local patch site. These symptoms are typically temporary and resolve either within a few days or upon discontinuation of NRT. Participants in this study may be eligible to receive NRT as per the standard of care provided by each participating quitline.

Participants who visit a dentist or increase their routine brushing and flossing may experience mild and temporary discomfort or gum bleeding (e.g., from tooth cleaning or flossing). This will resolve with continued regular oral hygiene.

2.3.2 Potential Benefits

Participants may quit smoking. As a result, they may reduce their risk of chronic disease onset or exacerbation, save money, and benefit from the good feeling of knowing that they are tobacco free.

Participants who see a dentist or change their routine oral health care can reduce their risk for future oral disease, may experience improved cosmetic appearance and self-esteem, and may experience reduced halitosis or tooth stains.

All participants in the experimental arm may benefit from increased awareness of proper oral hygiene behaviors and receipt of provided oral hygiene tools (e.g., toothbrush, floss, etc.). Those who also change other relevant behaviors such as limiting or reducing sugary beverages and alcohol use or increasing fruit and vegetable intake could experience additional positive health effects. The positive health effects include better oral health, reduced weight, and/or reduced risk of chronic disease onset or exacerbation.

All participants, regardless of intervention arm, may benefit from the sense of well-being associated with contributing to research.

3 OBJECTIVES

3.1 Study Objectives

The primary objective of this study is to assess the effects of the proposed behavioral intervention on tobacco abstinence and utilization of professional dental services.

The secondary objectives of this study include:

- Assess the impacts of the enhanced intervention on key secondary behavioral outcomes and select intermediate outcomes/process measures that could mediate treatment effects.
- Determine the effectiveness of the proposed enhanced intervention, whether it warrants dissemination to smokers through tobacco quitline programs nationally in the current form, or whether further refinement and evaluation are warranted.
- Calculate the incremental cost of adding the Oral Health 4 Life program to usual quitline care and create a decision support tool that quitline sponsors (i.e., potential purchasers of the program) can use to inform decisions about whether to offer the program.

The results of this project will inform whether the proposed intervention warrants further evaluation or dissemination through tobacco quitlines based on its effectiveness and help purchasers make informed decisions about providing the program.

The intervention will be offered to people seeking treatment for smoking cessation through one of the participating state-funded tobacco quitlines and will reach a high-need, lower-income population who are eligible for these free services.

Additional detail on the proposed enhanced intervention is included in sections 6 and 7.

3.2 Study Outcome Measures

Study outcome measures are discussed below. Copies of the baseline and follow-up assessment measures are included in Appendices B and C.

3.2.1 Primary

Smoking abstinence. Per convention, this will be assessed by a self-report of no smoking, even a puff, in the past 7 days assessed at 6 month follow-up (i.e., 7 day point prevalent abstinence). Missing data will be imputed using a worst case scenario in which individuals with missing outcomes will be assumed to be smoking for the main outcome analyses.

Professional dental care in the past 6 months. This will be assessed by a self-report of professional dental care in the past 6 months at the 2 or 6 month follow-up using the a standardized National Health Interview Survey (NHIS) item. Missing data will be imputed using a worst case scenario in which individuals with missing outcomes will be assumed to have not seen the dentist for the main outcome analyses.

We will use a ‘bogus pipeline’ strategy to encourage valid self-reported dental care utilization. Per this standard social psychology methodology, participants are told in advance their answers may be verified (e.g., we may contact their provider), thereby promoting more truthful reporting. We will also inform participants we are collecting the names and contact information for their dental care providers, again to discourage false reporting of service utilization (see scripting in follow-up surveys, Appendix C).

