3.2.2 Secondary

Secondary behavioral outcomes and process variables of interest are:

- **Smoking abstinence** assessed at 2 month follow-up (7 day point prevalent abstinence [PPA] with missing cases imputed). Additionally, we will assess abstinence at 2 and 6 months using a complete case (respondent only) analysis where missing data values are not imputed, to determine if imputation has a meaningful effect on the study results.
- We will assess whether groups differ in terms of the proportion of participants who either seek professional dental care following enrollment or have a future appointment scheduled at 6 months.
- Change in **oral health knowledge** from baseline to 2 and 6 month follow-up will be assessed using a scale adapted from Brennan et al⁴⁵ to address oral health behaviors (as opposed to tooth decay); include smoking, alcohol use, sugar free gum, and fruits and vegetables intake; and modify scripting for better phone delivery.
- Change in self-reported **self-efficacy** and **motivation** from baseline to 2 and 6 month follow-up. Self-efficacy and motivation will be assessed using a 5 point Likert-type scale.

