5 STUDY ENROLLMENT AND WITHDRAWAL

5.1 Subject Inclusion Criteria

In order to be eligible to participate in this study, a participant must meet all of the following criteria (see also Eligibility Screen in Appendix D):

- Male or female, aged 18 or older
- Eligible for multi-call services through a participating tobacco quitline [in Louisiana, Nebraska, or Oregon] managed by Alere Wellbeing
- Can read and speak in English
- Able to comfortably read small print (i.e., no significant visual impairments that limit ability to read the intervention materials)
- Current daily smoker and smokes at least 5 cigarettes a day
- Interested in quitting smoking in next 30 days
- Have some or all natural teeth
- Have not visited a dentist for a checkup or teeth cleaning in the past 6 months and do not have an appointment scheduled in the next 6 months
- Has a cell phone capable of receiving text messages and provides cell phone number
- Has internet access for personal use
- Willing to talk about ways to improve their oral health
- Provides verbal consent to participate

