12 STATISTICAL CONSIDERATIONS

12.1 Study Hypotheses

All hypotheses tested will be evaluations of superiority of the enhanced intervention (UC cessation counseling + oral health promotion program) compared to UC (UC cessation counseling). Null hypotheses assume that participants in the enhanced intervention group are equal to the participants in the UC group. We hypothesize that, compared to people in the UC arm, participants in the enhanced intervention will:

- a. Be more likely to quit smoking as evidenced by 7 day PPA rates at 6 month follow-up (primary outcome) and at 2 month follow-up (secondary outcome)
- b. Be more likely to see a dental care professional in the past 6 months at 6 month follow-up [primary outcome] or at least be more likely to seek dental care or have scheduled a future appointment [secondary outcome].
- c. Exhibit more positive change in relevant oral health knowledge/beliefs and attitudes (e.g., self-efficacy, motivation) that could influence future behavior change [secondary outcomes].

We hypothesize that positive change in participants' knowledge, attitudes, and beliefs at 2 months will mediate positive change in the primary outcome behaviors at 6 months; and that the Oral Health 4 Life program will be acceptable to quitline callers

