individuals using generalized estimating equations.¹ To assess differences in dental care utilization, we will compute whether participants saw a dentist post-enrollment using data from each follow-up, then run a single logistic regression model. We will specify an independent working correlation structure and estimate robust standard errors to avoid making model assumptions about the variance. Models will use a logit link function for the binary primary outcomes and odds ratios will be used to quantify differences between groups. To improve precision and power, analyses will be adjusted for the following pre-specified baseline characteristics that are expected, based on prior knowledge, to be important predictors of outcome or missing data: sex, age, pharmacotherapy use (e.g., NRT), baseline cigarettes per day, depression history, self-efficacy, and motivation for quitting. Models will also adjust for variables used to stratify randomization (dental insurance coverage and state quitline).

To estimate the effects of the intervention on secondary outcomes (e.g., completing or scheduling a dental appointment, brushing, self-efficacy, motivation, etc.), we will apply similar regression models as described for the primary outcomes, using appropriate link functions dependent on outcome type, and further adjust for baseline outcome value when appropriate.

To handle missing follow-up data for the primary outcomes we will assume that missing subjects are smokers and are non-users of dental service. In sensitivity analyses, we will use modern imputation methods to impute missing outcome data, based on the observed pattern of missingness.² We also will conduct a respondent only missing data sensitivity analysis that only includes subjects with observed outcome data (i.e., a complete case analysis).

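### The primary dental outcome is not defined the same way throughout: section 3.2.1 uses a 6-month look-back that reaches before enrolment, section 12.4 counts only post-enrolment care, and the entry criterion does not close the gap

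*Combined protocol and SAP*

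**What the plan says.** The plan describes the primary dental outcome in three ways.

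- **Care after enrolment.** The Protocol Summary lists it as "Receipt of professional dental care following enrollment [yes/no", and the Précis agrees. The analysis derivation in section 12.4 is "we will compute whether participants saw a dentist post-enrollment using data from each follow-up". The related secondary outcome in section 3.2.2, a composite with future appointments, also counts from enrolment: "either seek professional dental care following enrollment or have a future appointment scheduled at 6 months".
- **A 6-month look-back at either survey.** Section 3.2.1, which defines the primary outcomes: "This will be assessed by a self-report of professional dental care in the past 6 months at the 2 or 6 month follow-up".
- **A 6-month look-back at the last survey.** The hypothesis in section 12.1: "Be more likely to see a dental care professional in the past 6 months at 6 month follow-up".

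Entry is also described in more than one way. The inclusion criterion in section 5.1 reads "Have not visited a dentist for a checkup or teeth cleaning in the past 6 months" and adds that no appointment may be scheduled in the next 6 months. The Population entry of the Protocol Summary describes "Those who have not used dental care services in the past 6 months" and refers the reader to sections 5.1 and 5.2. Section 12.2 says the eligibility rule means no participant will have seen a dentist in the 6 months before entry, and on that basis assumes a 5% rate in usual care.

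**The concern.** The three wordings can score the same person differently. Under section 3.2.1 taken literally, a yes at month 2 may refer to a visit made before randomisation, which the intervention cannot have caused. Under section 12.1 taken literally, a person who reports a visit at month 2 and has no 6-month survey becomes a non-user under the worst-case rule, while section 12.4 counts that person as a user.

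The look-back would do no harm if nobody could enter with recent dental care. Section 12.2 assumes this, but section 5.1 disqualifies only a checkup or cleaning, whereas the outcome is any professional dental care. A recent emergency or other non-routine visit therefore does not bar entry.

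This is one of two primary outcomes, and section 3.2.2.2 builds the cost per dental visit on it. It should have a single definition, fixed before results are seen by arm.

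**Working it through.** **Look-back windows.** Appendix A puts the first follow-up at about week 8. Section 7.3.2.5 allows 4 further weeks at the 2-month survey and 6 further weeks at the 6-month survey. Taking 6 months as 26 weeks:

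- Month-2 survey on time: 26 − 8 = 18 weeks before enrolment.
- Month-2 survey at the end of its window: 26 − (8 + 4) = 14 weeks before enrolment.
- 6-month survey on time: the look-back is essentially the time since enrolment, so sections 12.1 and 12.4 nearly agree.
- 6-month survey 6 weeks late: the look-back misses about the first 6 weeks after enrolment. Section 2.2 hopes to see cleanings around the quit date, which may fall in that period.

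**The plan's own power figures.** Inputs from section 12.2: two-sided alpha 0.05, normal approximation with pooled variance, no dropout inflation. Equal allocation follows the design schematic, so n = 718 gives 359 per arm. For the three dental rows of Table 2 at 90% power, this method gives total sizes of 856, 664 and 376, exactly as printed.

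For 5% vs 10.6% (the stated 5.6-point difference) at 359 per arm:

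- z = [(p2 − p1) − 1.96 √(2p̄(1 − p̄)/359)] / √([p1(1 − p1) + p2(1 − p2)]/359), with p̄ = 0.078
- z = (0.056 − 1.96 × 0.02002) / 0.01991 = 0.842, so power is 80.0%, as stated.
- The same formula gives 99.4% for 5% vs 15%.

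The sample size arithmetic is right for an outcome counted from enrolment.

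**Illustration if pre-enrolment visits were counted.** The documents give no rate, so the share q of participants affected is an assumption.

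- Take section 12.2's 5% per 6 months as the rate of any care. Over 3 months: 1 − 0.95^(3/6) = 2.5%. Over 4 months: 1 − 0.95^(4/6) = 3.4%.
- Assume a quarter to a half of that is not a checkup or cleaning. Then q runs from 0.25 × 2.5% = 0.6% to 0.5 × 3.4% = 1.7%.
- Each arm's observed rate becomes q + (1 − q)p.

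| q | True 5% vs 10.6%: observed rates | Power | True 5% vs 15%: power |
|---|---|---|---|
| 0 | 5.00% vs 10.60% | 80.0% | 99.4% |
| 0.6% | 5.57% vs 11.14% | 77.0% | 99.2% |
| 1.7% | 6.62% vs 12.12% | 71.7% | 98.6% |

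The calculation applies q to everyone. Only people who answer the month-2 survey could report a visit this way, so the losses lean high for a given q. If screening in fact excluded all recent care, or scoring is limited to post-enrolment visits, q is about 0 and the stated power stands.

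**The case against.** The strongest reply is that section 12.4 already settles the analysed variable: post-enrolment care, from both surveys, in agreement with the Protocol Summary. Section 3.2.1 can be read as naming the survey item, a standardised national survey question, from which section 12.4 then derives the outcome. Section 12.1 is a hypothesis and not a scoring rule, and the Population entry defers to section 5.1.

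Much of this stands. The intended variable is clear, and no scoring or analysis text directs that a month-2 yes be discarded. Two things remain. Section 12.4 gives no rule for placing a month-2 answer about the past 6 months after enrolment; section 3.2.1 mentions collecting provider names and contact details but not visit dates. And section 12.2's eligibility statement does not follow from section 5.1.

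A reader might infer four stronger conclusions that the documents do not support.

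- *Pre-enrolment visits will be counted.* That would need an item not anchored to enrolment, no date restriction in scoring, and entry of people with recent non-routine care, all together. Appendix C is not shown, and section 12.4's target speaks against the second condition.
- *Section 12.1 loses early visits in general.* Anyone surveyed on time at 6 months still reports them. Loss needs a missing or late survey.
- *Cost per dental visit would be inflated in proportion to visits lost.* Section 3.2.2.2 values a visit at a mean reimbursed amount, which does not scale that way.
- *Section 5.1 makes entry stricter.* Its list of disqualifying visits is shorter, so entry is wider on that point; its no-appointment condition is a separate restriction.

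**Conclusion.** The inconsistency is certain on the text, and section 3.2.1 is the larger mismatch. Whether anyone would be misclassified cannot be determined from the documents. If it happened, randomisation makes it similar in both arms, so it would dilute the effect and cost some power without producing a false positive.

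Under the assumed 0.6% to 1.7%, the loss is about 3 to 8 percentage points of power at the smallest difference the plan cites (80% to between 77% and 72%). It is under 1 point at the 5% vs 15% effect that section 12.2 highlights. Those figures depend on applying the 5% rate to the pre-enrolment period and on the assumed non-routine share. Severity is minor to moderate.

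**What to change.** - Reword sections 3.2.1 and 12.1 to the definition in the Protocol Summary and section 12.4: any professional dental care since enrolment, reported at either follow-up.
- Before outcomes are seen by arm, state how a month-2 yes to a past-6-months item is placed after enrolment, using visit dates if they are collected. Add one sensitivity analysis that does not count undated month-2 yes answers.
- State that the cost per dental visit in section 3.2.2.2 uses the same variable.
- Reconcile section 12.2 and the Population entry with section 5.1. If non-checkup care before enrolment was allowed and can be counted, qualify the 5% base rate and the dental power. This is a matter of reporting only: section 12.4 already gives 737 enrolled, and the abstinence outcome set the planned size.
- Do not change the survey item partway through follow-up; that would make a primary outcome non-uniform across participants.

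The cost is a few wording changes, one scoring sentence and one extra analysis. No new data or larger sample is needed. The qualified dental power may look slightly less favourable.
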